Subjects will undergo metabolic and endocrine testing at the end of Period 1 and at the end of Period 2. Certain tests will also be performed at earlier time points during Period 2, in order to clarify the time course of leptin initiation and withdrawal on these outcomes. Explanations for the timing of these tests are provided in the detailed test descriptions. A summary of the test schedule is in the table, below. Tests associated with Period 1 and the follow-up are highlighted in gray. The exact timing of each test may vary slightly due to practical scheduling issues. A sample patient calendar is given in Appendix A.

Study Day	Period 1					Period 2														
	-5	-4	-3	-2	-1	0	1	2	3	4	5	6	7	8	9	10	11	12	13	14
Metabolic Chamber					x							x						x		
24 hr urine					x							x						x		
DEXA						x													x	
Skin temperature			x		x						x					x		x		
Exercise test			x								x					x				
Resting Energy Expenditure	x			x			x				x				x		x			
Blood pressure monitoring				x	x	x	x										x	x		
Heart rate monitoring				x	x	x	x										x	x		
Euglycemic Clamp				x													x			
Glucose & lipid turnover				x								x					x			
LH pulsatility			x														x			
MRI/MRS				x													x			
Fasting research blood tests	x				x	x		x		x		x		x		x		x	x	
Safety labs	x				x	x		x		x		x		x		x		x	x	
Actigraphy			x	x	x	x	x	x	x	x	x	x	x	x	x	x	x	x	x	
Vital signs	x	x	x	x	x	x	x	x	x	x	x	x	x	x	x	x	x	x	x	x
Anthropometrics	x					x													x	
Bedside glucose monitoring	x	x	x	x	x	x	x	x	x	x	x	x	x	x	x	x	x	x	x	x
Pregnancy test	x																x			
Echocardiogram		x																		
Ultrasounds	x			x																
OGTT	x																			

Long-term follow-up

Certain effects of leptin may not be detectable, or may be submaximal, within the 2-week intervention period in this study. These include changes in liver steatosis and insulin sensitivity. For this reason, we wish to study the longer-term (6 months) effects of leptin in subjects participating in this study. Therefore, we plan to restudy subjects in the leptin naïve group and bring them in for follow-up 6 months (range, 5-9 months) after starting leptin. Given budgetary and logistical issues, foreign patients may be seen for follow-up 12 months after initiating leptin therapy. We will ask them to obtain lab work locally and send us the results. It will not be possible to maintain an isocaloric diet for 6 months after leptin initiation in the free-living environment.

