10. Glucose and Lipid Turnover: Stable isotope tracers will be used to measure glucose and lipid turnover. Endogenous glucose production will be measured using steady-state infusion of [6,6-²H₂] glucose tracer. The fractional rate of gluconeogenesis will be measured using steady-state oral dosing of deuterated water (²H₂O)⁴⁹. The rate of lipolysis will be measured using steady-state infusion of deuterium-labeled ²H₅-glycerol, and the fatty acid turnover rate will be measured using steady-state infusion of [U-¹³C₁₆] palmitate. Subjects will fast after 8 pm. A total of 3 grams per kg lean body mass of ²H₂O will be given in four divided doses every two hours at 9 pm, 11 pm, 1 am, and 3 am in order to enrich the subject’s body water pool to approximately 0.5% ²H₂O. Beginning at ~5 am, a primed [6,6-²H₂]glucose infusion will be given for 3 hours, after which blood samples to measure isotope enrichment will be measured over a period of 30 minutes at steady state. Two hours after the [6,6-²H₂]glucose infusion begins, a primed ²H₅-glycerol infusion, and unprimed [U-¹³C₁₆] palmitate infusion will be given for one hour, and

isotope enrichment will be measured over a period of 30 minutes at steady state. Tracer studies will be performed at the end of Period 1, in the middle and end of Period 2, and during the follow-up visit for subjects in the leptin-naïve group. To assess the effects of hyperinsulinemia on glucose turnover, the glucose tracer infusion will be continued during the euglycemic, hyperinsulinemic clamp study, below, with blood samples for tracer enrichment obtained during the steady-state period of the clamp.

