11. Euglycemic Hyperinsulinemic Clamp: This is the gold-standard test to measure insulin sensitivity. For insulin treated subjects, an overnight insulin drip may be given beginning at 6 pm the night prior to the clamp to maintain euglycemia. After an 8-hour fast, insulin will be infused at a dose of 120 mcU/m²*minute. This dose is designed to suppress endogenous glucose production and near-maximally stimulate glucose uptake in this group of very insulin resistant subjects. For a small number of subjects with extreme insulin resistance (requiring more than 200 units of insulin per day), higher doses of insulin may be used during the clamp study to create a state of hyperinsulinemia above the subject's baseline state. 20% dextrose enriched with 2.5% [6,6-²H₂] glucose tracer will be infused at a variable rate to maintain blood glucose at approximately 90 mg/dL. If subjects remain hyperglycemic without dextrose infusion after 1 hour of insulin infusion (by which time maximum insulin effect is expected), the clamp will be considered "failed" and will be prematurely terminated. During the insulin infusion, blood samples (0.5 mL) will be obtained every 5 minutes to measure blood glucose at the bedside. At steady state, the rate of dextrose infusion provides an estimate of insulin-stimulated glucose disposal. Additional samples will be drawn to measure the glucose and lipid tracers (described above), insulin, and other hormone levels. Due to the blood volumes and inconvenience of this test to participants, it will be performed once at the end of Period 1, once at the end of Period 2, and during the follow-up visit for subjects in the leptin-naïve group. If technical problems occur with a clamp study (e.g. IV failure or failure to attain steady-state glucose and insulin levels), the clamp may be repeated if blood volume limits permit.

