lipid CH2 and CH3 resonances lipid and the T2 of water are measured with five quick expiration breath hold non-WS spectra averaging two signals each at TR 3s and TE 24, 36, 48, 96 and 144 ms. These T2 values are used to correct the water and total lipid signals for signal decay in the 35 ms echo delay. Fat fraction is then calculated as from the T2 corrected signals S_{water} and S_{lipid} as: fat fraction = S_{lipid}/(S_{water}+S_{lipid}). Visceral and subcutaneous fat measurements will be obtained using standard T1 Spin Echo technique which presents fat as a bright signal that can be segmented for area and volume measurements.

15. 24 hour urine studies: Urine will be collected during each stay in the metabolic chamber (at the end of Period 1, in the middle and end of Period 2, and during the follow-up visit for subjects in the leptin-naïve group). Samples will be analyzed for nitrogen excretion to assess macronutrient oxidation, as well as excretion of glucose, protein and minerals.
16. Oral glucose tolerance test: After a 12-hour fast preceding the test, subjects will be given 75 gram (1.75gm/kg in pediatric patients less than 40kg) oral glucose solution. Venous glucose, plasma insulin and free fatty acid levels (3 cc blood to be drawn at each draw) will be obtained from blood samples drawn at -10, 0, 30, 60, 90, 120 and 180 minutes during the oral glucose tolerance test.

Endocrine Evaluation

1. LH pulsatility will be assessed using overnight sampling. Blood will be sampled from an indwelling IV catheter every 10 minutes between 11 pm and 7 am. Arithmetic mean levels for LH will be calculated. Analysis of pulsatile secretion of LH will be determined using a modification of the Santin and Bardin Method⁵⁰, which requires a 20% increase from nadir to peak LH concentrations for pulse detection. LH pulse frequency will be determined by calculating the number of LH pulses during the sampling interval. LH pulse amplitude will be calculated from the difference between the nadir and peak hormone levels. Due to the blood volume requirements of this test, it will be performed once at the end of Period 1, once at the end of Period 2, and during the follow-up visit for subjects in the leptin-naïve group.

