Suspected transmission of an infectious agent (eg, pathogenic or nonpathogenic) via the study drug is an SAE. Although pregnancy, overdose, cancer, and potential drug induced liver injury (DILI) are not always serious by regulatory definition, these events will be handled as SAEs (per Aegerion Pharmaceuticals request via United Biosource Corporation, the CRO contracted by Aegerion to perform Pharmacovigilance activities on their behalf).

NOTE:

The following hospitalizations are not considered SAEs:

- a visit to the emergency room or other hospital department < 24 hours, that does not result in admission (unless considered an important medical or life-threatening event)
- elective surgery, planned prior to signing consent
- admissions as per protocol for a planned medical/surgical procedure

- routine health assessment requiring admission for baseline/trending of health status (eg, routine colonoscopy)
- medical/surgical admission other than to remedy ill health and planned prior to entry into the study. Appropriate documentation is required in these cases
- admission encountered for another life circumstance that carries no bearing on health status and requires no medical/surgical intervention (eg, lack of housing, economic inadequacy, caregiver respite, family circumstances, administrative reason).

Pregnancy

All pre-menopausal women included in the study will be asked to use an effective method of contraception. If necessary, a gynecology consultation will be obtained to assist the patients to choose an appropriate method of contraception.

Should a patient become pregnant while taking metreleptin, metreleptin may be continued during pregnancy under the following circumstances:

1. The investigators feel that metreleptin withdrawal would constitute a harm to mother and fetus.
2. The patient understands that the effects of metreleptin in pregnancy are unknown, and wishes to continue.
3. The patient receives prenatal care from a high-risk obstetrician experienced in managing diabetes during pregnancy. Management of diabetes must be the primary responsibility of the patient's local health care providers, although the NIH study team will provide advice as appropriate regarding metreleptin use and use of concentrated insulin (U-500) if necessary.
4. The patient and her local health care team agree to remain in close contact with the NIH study team and respond to requests for clinical information needed to document the course of pregnancy and its outcome.

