Appendix A: Sample Patient Calendars

Short-term portion of study (leptin naïve and leptin treated subjects)

Study Day	Period 1							Period 2													
	-6	-5	-4	-3	-2	-1	0	1	2	3	4	5	6	7	8	9	10	11	12	13	14
Time																					
6:00																					
6:30																					
7:00																					
7:30																					
8:00																					
8:30																					
9:00	Oral Glucose tolerance Test	Start Actigraph	Pelvic Ultrasound																		
9:30																					
10:00																					
10:30																					
11:00																					
12:00																					
13:00	Admit	VAS (p-lunch)	VAS (p-lunch)	VAS (p-lunch)	VAS (p-lunch)	VAS (p-lunch)	VAS (p-lunch)	VAS (p-lunch)	VAS (p-lunch)	VAS (p-lunch)	VAS (p-lunch)	VAS (p-lunch)	VAS (p-lunch)	VAS (p-lunch)	VAS (p-lunch)	VAS (p-lunch)	VAS (p-lunch)	VAS (p-lunch)	VAS (p-lunch)	VAS (p-lunch)	
14:00																					
15:00																					
16:00																					
17:00																					
18:00																					
19:00																					
20:00	Exercise	Exercise	Exercise	Exercise	Exercise	Exercise	Exercise	Exercise	Exercise	Exercise	Exercise	Exercise	Exercise	Exercise	Exercise	Exercise	Exercise	Exercise	Exercise	Exercise	Exercise
23:00					8 hr LH sampling														8 hr LH sampling		

AM O (IRB approved 5/14/2018)

13-DK-0057

Submitted for CR 2019: 1/11/2019

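### LH pulsatility: cycle phase and hormonal contraception are not handled, and the LH night shifts by one day relative to the clamp and chamber between Periods

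*Combined protocol and SAP*

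**What the plan says.** - **Measurement.** Endocrine Evaluation, item 1: "Blood will be sampled from an indwelling IV catheter every 10 minutes between 11 pm and 7 am", once at the end of each Period, and once more at follow-up in the leptin-naïve group.
- **Status.** Outcome Measures lists LH pulsatility among the additional outcomes. The power table under Sample Size Justification has no LH row.
- **Who is sampled.** Both sexes, aged 14 to 70, with no criterion on menstrual or menopausal status. The Pregnancy section says "All pre-menopausal women included in the study will be asked to use an effective method of contraception" and does not specify the type. Pre-study Medications continues existing drugs other than insulin through both Periods.
- **Analysis.** Paired end-of-Period comparisons, separately by group, aiming at 10 completers per group. Analysis of Primary Outcomes names sex as a potential covariate, but not cycle phase, menopausal status or sex-steroid use.
- **Timing.** The schedule table under Study Procedures marks LH on Days -3 and 11, clamp and tracer study on Days -2 and 11 (with a further tracer study on Day 6), chamber on Days -1, 6 and 12, and exercise test on Days -3, 5 and 10. It adds: "The exact timing of each test may vary slightly due to practical scheduling issues". The short-term calendar in Appendix A, as extracted, shows LH starting at 23:00 on Days -2 and 12.

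**The concern.** The gonadal axis is a stated target of the study, and LH pulsatility is the only measure listed under the endocrine outcomes. Each subject contributes one night per condition, without a replicate. Two things other than leptin can act on the difference between the nights.

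The first is reproductive status. LH pulse frequency and amplitude vary with cycle phase, and hormonal contraception suppresses them. This is standard physiology, which the documents do not discuss. A fixed 14-day gap in women whose phase is not recorded brings in a phase difference. Hormonal users bring in differences near zero.

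The second is position in the test sequence. The night before a tracer study carries labelled-water doses, "given in four divided doses every two hours at 9 pm, 11 pm, 1 am, and 3 am", and the night before a clamp may carry an insulin drip. If the LH night moves relative to these tests, the two nights are not taken under the same conditions.

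At stake is whether a reported LH change, or its absence, says anything about leptin with about 10 subjects per group.

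**Working it through.** The documents give no effect size, SD or power for LH, so there is no stated figure to reproduce. The checks use the schedule and simple cycle arithmetic.

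**1. Intervals between Periods (schedule table)**

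- LH: 11 - (-3) = 14 days
- Clamp and tracer study: 11 - (-2) = 13 days
- Chamber: 12 - (-1) = 13 days
- Exercise test: 10 - (-3) = 13 days

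The LH night therefore moves by 14 - 13 = 1 day relative to each of these tests. This does not depend on what the mark means.

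**2. Where the night falls**

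- *Mark is the start evening.* Period 1: night -3/-2, ending on the clamp morning. Period 2: night 11/12, starting after the clamp and ending on the chamber day. Only the Period 1 night overlaps the labelled-water doses and any insulin drip.
- *Mark is the end morning.* Period 1: night -4/-3, ending a day before the clamp. Period 2: night 10/11, ending on the clamp morning. The overlap is then in Period 2 only.
- *Appendix A days (-2 and 12) against the table's clamp days.* The Period 1 night starts on the clamp evening; the Period 2 night starts on the evening after the clamp day, which is the chamber day. Both follow the clamp, by different intervals.

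The follow-up calendar in Appendix A has LH from 23:00 on Day 1 into Day 2, exercise test on Day 2, clamp on Day 3 and chamber on Day 4. Long-term follow-up says this visit copies Period 1 testing. Matching exercise, clamp and chamber to Days -3, -2 and -1 puts the LH night at -4/-3, which favours the end-morning reading.

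**3. Cycle phase**

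Assumptions: cycle length L of 24, 28 or 35 days, and a second phase of 14 days. The gap as a fraction of the cycle is 14/L. For each of the L possible start days, check whether the day 14 days later is in the other phase.

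| L | 14/L | start days with different phases |
|---|---|---|
| 24 | 0.58 | 20/24 = 83% |
| 28 | 0.50 | 28/28 = 100% |
| 35 | 0.40 | 28/35 = 80% |

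In each row half of the discordant start days run from first to second phase and half the other way (10 and 10, 14 and 14, 14 and 14). If admission is unrelated to phase, the expected shift is zero and the effect is extra variance. If phase moves LH by ±φ in k discordant women out of n = 10, the variance of the group mean rises by kφ²/n² = kφ²/100. The documents give neither φ nor k.

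**4. Hormonal contraception**

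If a share p of a group contributes no change and the rest change by δ, the observed mean is (1 - p)δ. For p = 20% this is 0.80δ; for p = 40% it is 0.60δ. The range for p is an assumption.

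**5. Sampling load**

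8 h × 60 / 10 = 48 intervals, so 49 samples if both ends are drawn, and 2 × 49 = 98 over two nights. The LH sample volume is not given, so the blood saved by omitting a subject cannot be sized.

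**The case against.** Three stronger readings are tempting, and the documents do not support them.

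- *LH change cannot be read as a leptin effect at all.* Men, post-menopausal women and other non-cycling women are eligible and are not affected by phase. Regular cycles are themselves an assumption in a population in which leptin is said to normalize reproduction. Admission is not tied to phase, so phase mainly adds noise. Contraception is not stated to be hormonal, and existing drugs continue on both nights, so constant use can dilute an effect but not mimic one.
- *The LH nights lie on opposite sides of the clamp.* This needs the start-evening reading, which the follow-up calendar does not favour. The short-term calendar cannot settle it: as extracted, it is broken, with the glucose tolerance test at 9:00 on the day of a 13:00 admission and no clamp, tracer or chamber entries.
- *The primary measurements are damaged by a sampling night.* Nothing in the documents shows or sizes this.

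The plan also has partial safeguards. Sex is a potential covariate. Exclusion 16 covers drugs that interfere with interpretation. The two groups undergo opposite leptin changes, so a position artefact would keep its sign while a leptin effect should reverse.

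These points limit the concern without removing it. Exclusion 16 does not name sex steroids, and a sex covariate does not separate cycling from non-cycling women. Groups are analysed separately and their comparison is exploratory. The allowance for slight variation in timing does not remove a one-day offset built into the schedule.

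**Conclusion.** The point holds in two limited parts.

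1. In cycling women and in hormonal contraceptive users, an LH change within a group cannot be cleanly attributed to leptin. On cycles of 24 to 35 days with a 14-day second phase, 80% to 100% of start days give different phases on the two nights, mainly as added variance. Hormonal users dilute the mean in proportion to their share, which is unknown.
2. The LH night sits one day differently relative to clamp and chamber in the two Periods. The offset is certain from the schedule table; the side of the clamp on which each night falls is not.

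The consequence is a noisier, possibly diluted and position-shifted LH comparison with about 10 completers per group. LH is an additional outcome without a power claim, and the primary outcomes and their conclusions are not shown to be affected.

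**What to change.** - At admission, record last menstrual period and any sex-steroid or hormonal contraceptive use.
- Leave subjects on hormonal contraception or other sex steroids out of LH sampling, or at least out of the LH analysis.
- Report LH separately for men, non-cycling women and cycling women, with cycling women described by phase and not tested.
- State whether the table mark is the start evening or the end morning.
- Move one LH night by a day so that its position relative to clamp and chamber is the same in both Periods. The gap becomes 13 days, which does little for phase (13/28 = 0.46), so the first three changes are still needed.
- Reconcile the schedule table with both Appendix A calendars.

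The cost is protocol wording, a one-day shift, and fewer subjects in an LH analysis that is already small. Omitting the sampling spares about 98 samples per excluded subject over the two nights. That may help where "the clamp may be repeated if blood volume limits permit" applies, by an amount that the documents do not allow one to calculate.

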This is an exploratory study of the energy-intake independent effects of leptin initiation and withdrawal in lipodystrophy. Preliminary data are not available to generate estimates of power for each outcome to be tested. The primary comparisons to be tested for each outcome of interest are results at the end of Period 1 versus the end of Period 2, analyzed separately for each group of subjects (leptin-naïve versus leptin treated). Thus, sample size calculations are based on paired, before and after, comparisons within each group of subjects. The data and references used for power calculations are shown in the table, below. Data in the table using the 10% weight loss model are given as percent change from pre-weight loss values, while data from lipodystrophy patients are given as absolute differences between leptin treated and untreated states. All calculations assumed a sample size of 10 and an alpha of 0.05, without correction for multiple comparisons. Because the standard deviations (SDs) of differences between on and off leptin conditions were not reported in publications, the SDs of the difference (used to calculate power for paired comparisons) was estimated in two ways: First, the SDs of differences are calculated by assuming that the SDs of on and off leptin reported in the literature are independent (Power 1 in the table). Second, a “worst-case scenario” was assumed that the SDs on and off leptin in the literature are perfectly positively correlated (Power 2 in the table). The first scenario is the commonly used method, while the second case is the most conservative calculation.

Outcome	Model	Duration of leptin	Off-leptin mean (SD)	On-leptin mean (SD)	Power 1	Power 2
Total energy expenditure ¹¹ (% Δ in kcal/day)	10% wt loss	5 wk	-22% (15.8)	-6% (4.7)	0.92	0.79
Skeletal muscle work efficiency ¹¹ (% Δ in kcal/min expended during exercise vs. at rest)	10% wt loss	5 wk	20% (12.6)	3% (2.5)	0.99	0.97
Resting energy expenditure ²⁴	lipodystrophy	4 mo	35.5 (8.2)	33.6 (6.7)	0.14	0.11
T3 ¹¹ (% Δ)	10% wt loss	5 wk	-9% (6.3)	3% (3.2)	0.99	0.99

T3 ⁴³ (nmol/L)	lipodystrophy	4 mo	124 (37)	114 (26)	0.18	0.13
T4 ¹¹ (% Δ)	10% wt loss	5 wk	-7% (7.9)	-1% (1.3)	0.77	0.66
fT4 ⁴³ (pmol/L)	lipodystrophy	4 mo	1.05 (0.15)	1.03 (0.15)	0.09	0.08
TSH ⁴³ (μU/mL)	lipodystrophy	4 mo	1.37 (0.37)	1.24 (1.1)	0.10	0.09
Norepinephrine ¹¹ (% Δ)	10% wt loss	5 wk	-12% (15.8)	-7% (12.6)	0.19	0.14
Epinephrine ¹¹ (% Δ)	10% wt loss	5 wk	-40% (35)	28% (47)	0.98	0.83

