Appendix A: Sample Patient Calendars

Long-term follow-up (leptin naïve subjects, only)

Study Day	0	1	2	3	4	5
Time						
5:00						
6:00		Fasting labs	LH sampling			
6:30						
7:00		OGTT (NPO)	REE		Start 24 hr urine	Stop 24 hr urine
7:30					Start skin temp	DEXA
8:00					Chamber	
8:30						Stop skin temp
9:00			Start Actigraph			Stop Actigraph
9:30			Skin temp monitor	Clamp		
10:00			Exercise test			
10:30						Discharge
11:00			Skin temp monitor			
12:00						
13:00	Admit					
14:00						
15:00						
16:00						
17:00			Start HR monitor	Stop HR monitor		
18:00				Start BP monitor	Stop BP monitor	
19:00						
20:00						
23:00		8 hr LH sampling				

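### The overnight LH-sampling session does not hold the same position relative to the clamp/tracer day and the metabolic chamber in the two Periods that the primary analysis compares

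*Combined protocol and SAP*

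**What the plan says.** **LH sampling.** Endocrine Evaluation, item 1: "Blood will be sampled from an indwelling IV catheter every 10 minutes between 11 pm and 7 am". On frequency: "it will be performed once at the end of Period 1, once at the end of Period 2", and again at follow-up in the leptin-naïve group.

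**Schedule table (Study Procedures).** The row "LH pulsatility" is marked on Days -3 and 11. "Euglycemic Clamp" is marked on Days -2 and 11, "Glucose & lipid turnover" on Days -2, 6 and 11, and the metabolic chamber on Days -1, 6 and 12. The text above the table allows small shifts for practical reasons.

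**Comparison.** Sample Size Justification defines the primary comparison as "results at the end of Period 1 versus the end of Period 2", made separately in each group. The three primary outcomes are clamp glucose disposal, tracer-measured lipolysis and 24-hour energy expenditure in the chamber.

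**Other overnight procedures.** Before each tracer study deuterated water is "given in four divided doses every two hours at 9 pm, 11 pm, 1 am, and 3 am", and a glucose tracer infusion starts at about 5 am (Metabolic Testing, item 10). Blood pressure is read by cuff every 30 minutes (item 5), with table marks on Days -2, -1, 0, 1, 11 and 12.

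**Calendars (Appendix A).** The follow-up calendar has "8 hr LH sampling" at 23:00 on Day 1 and LH sampling again at 6:00 on Day 2. It therefore labels the night by its start.

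**The concern.** Each primary test is a before/after comparison within subjects, with no concurrent control. The Diet section relies on each subject serving as his or her own comparator. That isolates leptin only if the two measurements are taken under the same conditions apart from leptin.

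An eight-hour night of blood draws every 10 minutes is a condition of measurement. If it comes just before a primary measurement at one time point and not at the other, the on/off-leptin contrast also contains whatever that night does to the measurement. Because the order is fixed by the schedule, every subject carries the same difference and averaging over subjects does not remove it.

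**Working it through.** The plan states no figure on this point. The check concerns the order of tests.

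**Step 1. Spacing, from the schedule table.**

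| Test | End of Period 1 | End of Period 2 | Gap in days |
|---|---|---|---|
| Exercise test | -3 | 10 | 10 - (-3) = 13 |
| Clamp, tracers, resting energy expenditure, MRI/MRS | -2 | 11 | 11 - (-2) = 13 |
| Chamber, 24-hour urine | -1 | 12 | 12 - (-1) = 13 |
| DEXA | 0 | 13 | 13 - 0 = 13 |
| LH sampling | -3 | 11 | 11 - (-3) = 14 |

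LH sampling alone is out of step, whatever its mark means. The short-term calendar in Appendix A, as far as its columns can be read, has LH at 23:00 on Days -2 and 12. That is one day later than the table in each Period, but again 12 - (-2) = 14 days apart.

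**Step 2. Which measurements directly follow an LH night.** Clamp, tracer and chamber days are taken from the table.

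| Reading | LH nights (day/day) | Before clamp/tracers: Day -2, Day 11 | Before chamber: Day -1, Day 12 |
|---|---|---|---|
| Mark = 11 pm start | -3/-2 and 11/12 | yes, no | no, yes |
| Mark = morning sampling ends | -4/-3 and 10/11 | no, yes | no, no |
| Appendix A days, 11 pm start | -2/-1 and 12/13 | no, no | yes, no (sampling falls inside the Day 12 stay) |

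The first reading matches the follow-up calendar's convention and leaves all three primary contrasts unbalanced. The second leaves the clamp and tracer contrasts unbalanced, with the opposite sign. No reading balances all three.

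**Step 3. Other overnight burdens.** Deuterated-water dosing precedes both Day -2 and Day 11. Cuff readings marked on Days -2/-1 and 11/12 cover the night before both compared chamber stays. These are balanced; the LH sampling is not. On the first reading, the Period 1 sampling also overlaps the 11 pm, 1 am and 3 am water doses and the 5 am tracer start, and the Period 2 sampling does not.

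**Step 4. Can the analysis separate it?** The covariates in Analysis of Primary Outcomes are pre-diet baseline values, age, sex, race, percent body fat, lean mass, weight, lipodystrophy type, endogenous leptin and caloric intake. None concerns the LH night. Adding one would not help: if subjects follow the schedule, an LH-night indicator is identical to the Period indicator, or its complement, in each unbalanced two-point contrast.

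**Step 5. Scale, by assumption only.** Suppose leptin has no effect and the order difference shifts the mean paired difference by d standard deviations. With n = 10 and two-sided alpha 0.05, the paired t statistic is noncentral t with 9 degrees of freedom and noncentrality d × √10.

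| d (assumed) | Noncentrality | Probability of rejecting |
|---|---|---|
| 0 | 0 | 0.05 |
| 0.1 | 0.32 | 0.06 |
| 0.25 | 0.79 | 0.11 |
| 0.5 | 1.58 | 0.29 |
| 1.0 | 3.16 | 0.80 |

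Under the plan's independence assumption, the SDs of the difference from its power table are:
- insulin sensitivity (1-month row): √(0.79² + 1.1²) = 1.35, so 0.25 SD = 0.34 mg/kg/min
- total energy expenditure: √(15.8² + 4.7²) = 16.5, so 0.25 SD = 4.1 percentage points
- glycerol turnover: √(36² + 7²) = 36.7, so 0.25 SD = 9.2 µmol/kg fat mass/min

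Nothing in the documents says which row of d applies.

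**The case against.** **Sleep is interrupted in both Periods anyway.** This stands. A reader might infer that each primary outcome follows a disturbed night at one time point and a free night at the other. The documents do not support that: the water doses precede both clamp/tracer days and the cuff readings precede both chamber stays. What differs is an increment, drawn through an indwelling catheter, and the protocol does not say that subjects are woken.

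**The count depends on one table mark, and days are nominal.** Partly stands. That all three primary outcomes are affected requires the start-of-night reading. The Appendix A short-term calendar differs by a day. Its columns are unreliable in the text available (a 9:00 glucose tolerance test falls on the day of a 13:00 admission), so it cannot settle the matter. Permission for small shifts does not correct a nominal order that differs, and the 14-day gap holds on every reading.

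**The Day 6 data have no LH night before them.** This helps in part. For energy expenditure on the start-of-night reading, Day -1 against Day 6 is an on/off contrast with no LH night on either side. It has less leptin exposure, however, and Day 6 follows water dosing, because tracers share that day, without scheduled cuff readings. For lipolysis on that reading, the affected point is the Day -2 baseline, so Day 6 cannot repair the contrast. The clamp is not done on Day 6.

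**The two groups change leptin in opposite directions.** A shift common to both would cancel in a between-group comparison of changes. The plan keeps that comparison exploratory, because it expects initiation and withdrawal to differ.

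**No effect is shown.** This stands. A reader might infer that baseline insulin sensitivity is depressed, so that leptin's benefit looks larger after initiation and withdrawal looks milder. The documents give neither direction nor size, and under the end-of-night reading the sign would reverse.

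**Conclusion.** The schedule puts LH sampling in a different position relative to the compared tests in the two Periods: 14 days apart against 13. On the better-supported start-of-night reading this affects all three primary contrasts, as well as resting energy expenditure and MRI/MRS. On the end-of-night reading it affects the clamp and tracer contrasts but not the chamber.

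The imbalance is the added LH sampling alone. It is common to all subjects, coincides with leptin on/off, and cannot be separated by any planned covariate. Whether it biases the results, and which way, cannot be said from the documents. The rejection probabilities above are a scale for assumed shifts, not an estimate.

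This is a cheap improvement in freedom from bias, not evidence that the primary results are invalid.

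**What to change.** 1. Put the LH night in the same position relative to the clamp/tracer day and the chamber in both Periods. One way is to move the Period 2 mark from Day 11 to Day 10. The gap becomes 10 - (-3) = 13 days, and the order matches on either reading of the mark.
2. State in the table whether the mark is the start or the end of the night, and reconcile the schedule table with the Appendix A short-term calendar, checked in the original layout.
3. For subjects already studied, record the actual LH night and report the order difference as a limitation. Use the Day 6 chamber and tracer data as a sensitivity check, subject to the limits above: informative mainly for energy expenditure, and for lipolysis only if the mark means the end of the night.
4. Re-ordering the 6-month visit is optional. There the clamp falls on the day after the LH night ends, unlike Period 1 on the start-of-night reading. But that visit lies outside the primary contrast, and Long-term follow-up says it cannot address energy-intake-independent effects.

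**Cost.** One table cell and a calendar edit, with no added procedure, inpatient day or blood volume. The downside is that, on the start-of-night reading, an LH night then precedes both clamps. Moving the Period 1 mark to Day -2 instead (11 - (-2) = 13) would place it before both chamber stays. Either choice balances the comparison.
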